Appendix A

Covariates and Outcomes

Variable Name in EHR	Description	Variable type
PATIENT_ID	ID for each patient not related to patient information	ID
MOM_AGE	Mother's age at time of delivery	Baseline covariate
FINANCIAL_CLASS	Payor at time of delivery from Medipac (insurance level, might be like coverage) (i.e. name like 'UPMC HEALTH NETWORK', 'MED PLUS', 'BEST HEALTH CARE', etc)	Baseline covariate
HOSP_ROLLUP_GROUPING1	Payor at time of delivery from Medipac (insurance type) (i.e. specifies type of UPMC insurance, examples include 'UPMC Commercial', 'Other MA Managed', 'Other Commercial', etc)	Baseline covariate
HOSP_ROLLUP_GROUPING2	Medicare, Medicaid, Self-pay, or Commercial Insurance	Baseline covariate
HPFLAG	Payor at time of delivery from Medipac (UPMC Health Plan Member flag, 1= has UPMC Health Plan, 0=Doesn't have it)	Baseline covariate
PT_ZIP	Patient zipcode	Baseline covariate
AD_ZIP_4	Patient zipcode, location extension (+4)	Baseline covariate
ADI_NATRANK	Area deprivation index, national ranking (0 most deprived, 100 least deprived)	Baseline covariate
RACE	Race, as reported through UPMC	Baseline covariate
MOM_HEIGHT	mother's height at time of delivery (cm)	Baseline covariate
OB_GRAVIDITY	Number of pregnancies (includes current pregnancy, so if it's their first pregnancy, this will be a 1)	Baseline covariate
OB_PARITY	Number of previous deliveries (will be 0 if it's their first pregnancy)	Baseline covariate
OB_FULL_TERM	Number of previous full term pregnancies	Baseline covariate
OB_PREMATURE	Number of previous premature deliveries (prior to 37 gestational weeks)	Baseline covariate
OB_ABORTIONS	Number of previous abortions, including therapeutic/spontaneous abortions	Baseline covariate
OB_LIVING	Number of previous live deliveries	Baseline covariate
OB_SPONTANEOUS_AB	Number of previous miscarriage/spontaneous abortions	Baseline covariate
OB_THERAPEUTIC_AB	Number of previous therapeutic abortions	Baseline covariate
PREGRAVID_WEIGHT	mother's pre-pregnancy weight (kg)	Baseline covariate
GESTAGE_ATVISIT_DAYS	This is the gestational age of the pregnancy at the time of prenatal visit. Calculated using the estimated delivery date ((280-(EPISODE.OB_WRK_EDD_DT-pat_enc.contact_date))).	Baseline covariate
PREGSTART_OBESE	Obese BMI at first prenatal visit (binary variable)	Baseline covariate
PREGSTART_MORBIDOBSE	Morbidly obese BMI at first visit (binary variable)	Baseline covariate
PREGSTARTHTN	Chronic hypertension at first prenatal visit (binary variable)	Baseline covariate
PREGSTART_CKD	Chronic kidney disease at first prenatal visit (binary variable)	Baseline covariate
PREGSTART_DIAB	Type I or Type II diabetes at first prenatal visit (binary variable)	Baseline covariate

PREGSTART_ANXIETY	Diagnosed or active anxiety at first prenatal visit (binary variable)	Baseline covariate
PREGSTART_DEPRESSION	Diagnosed or active depression at first prenatal visit (binary variable)	Baseline covariate
PREGSTART_LIVER_DISEASE	Liver disease at first prenatal visit (binary variable)	Baseline covariate
PREGSTART_TOBACCOUSE	Tobacco use history, recorded at first prenatal visit (options are "yes", "never", "quit", "passive")	Baseline covariate
PREGSTART_O_PREEEXISTING HTN	Pre-existing hypertension in any of these forms or combinations, complicating pregnancy: essential hypertension, hypertensive heart disease, hypertensive chronic kidney disease, secondary hypertension, or unspecified hypertension. Diagnosed or listed as active problem at first prenatal visit. (binary variable); Definition came from EPIC codes	Baseline covariate
PREGSTART_O_PREGINDUCE DHTN_NOPROT	Gestational hypertension without significant proteinuria, could occur during any trimester, childbirth, or puerperium. Diagnosed or listed as active problem at first prenatal visit (binary variable);	Baseline covariate
PREGSTART_O_PREGINDUCE D_PROTEDEMA_NOHTN	Gestational edema, gestational proteinuria, or gestational edema with proteinuria. Diagnosed or listed as active problem at first prenatal visit (binary variable);	Baseline covariate
PREGSTART_O_PREECLAMPSIA	Preeclampsia diagnosed or listed as active problem at first prenatal visit (binary variable)	Baseline covariate
PREGSTART_O_SUPERIMPOSEDPREE	Preexisting hypertension with preeclampsia. Diagnosed or listed as active problem at first prenatal visit. (binary variable); Definition came from EPIC codes	Baseline covariate
PREGSTART_O_ECLAMPSIA	Eclampsia diagnosed or listed as active problem at first prenatal visit (binary variable)	Baseline covariate
PREGSTART_O_UNSPHTN	Unspecified maternal hypertension. Diagnosed or listed as active problem at first prenatal visit. (binary variable);	Baseline covariate
PREGSTART_O_ANYHTN	Pre-existing hypertension in any of these forms or combinations, complicating pregnancy: essential hypertension, hypertensive heart disease, hypertensive chronic kidney disease, secondary hypertension, or unspecified hypertension. Diagnosed or listed as active problem at first prenatal visit. (binary variable);	Baseline covariate
PREGSTART_O_CARDIOMYOPATHY	Disease of the circulatory system affecting any stage of pregnancy. Diagnosed or listed as active problem at first prenatal visit. (binary variable); Definition came from EPIC codes	Baseline covariate
PREGSTART_O_GDM	Gestational diabetes mellitus. Diagnosed or listed as active problem at first prenatal visit. (binary variable)	Baseline covariate
PREGSTART_MEDREPORTED	Medications reported at first prenatal visit (binary variable)	Baseline covariate
PREVIOUS_GDM	Previous GDM in a prior pregnancy, not including this current pregnancy (gestational diabetes) (binary variable)	Baseline covariate
PREVIOUS_OBANYHTN	Previous gestational hypertension in a prior pregnancy, not including this current pregnancy (binary variable)	Baseline covariate

PREVIOUS_PREECLAMPSIA	Previous preeclampsia in a prior pregnancy (binary variable)	Baseline covariate
AUTOIMMDX_PT20WKS	Previous gestational autoimmune disease prior to 20 weeks (in prior pregnancy) (binary variable)	Baseline covariate
PRIOR_SBBTW16AND34	Prior stillborn between 16 and 34 weeks in a prior pregnancy (binary variable)	Baseline covariate
PRIOR_LBBTW31AND36	Prior premature live birth between 31 and 36 weeks in a prior pregnancy (binary variable)	Baseline covariate
PRIOR_SBAFTER34	Prior stillborn after 34 weeks in a prior pregnancy (binary variable)	Baseline covariate
PRIOR_VPTBBTW222AND30	Prior very premature birth between 22 and 30 weeks in a prior pregnancy (binary variable)	Baseline covariate
PRIOR_STILLBORN	Prior stillborn (time period not specified) in a prior pregnancy (binary variable)	Baseline covariate
PRIOR_PPROM	Prior preterm premature rupture of membranes in a prior pregnancy (binary variable)	Baseline covariate
PRIOR_PPROMBEFORE37	Prior preterm premature rupture of membranes before 37 weeks in a prior pregnancy (binary variable)	Baseline covariate
HOSPITAL	which hospital they delivered at	Baseline covariate
SINGLETONS	1=singleton birth, 0=twins, triplets, etc (binary variable)	Baseline covariate
PREG_CONTACT_DATE	First visit in Epic while pregnant	Baseline covariate
EST_GEST_AGE_DAYS	gestational age at the time of birth	Primary outcome
MOM_DELIVERY_WT	weight of mother at time of delivery (kg)	Secondary outcome
PREGANY_DEPRESSION	Diagnosis of depression or active depression at some point during pregnancy (would also be 1 if PREGSTART_DEPRESSION is 1) (binary variable)	Secondary outcome
PREGANY_ANXIETY	Diagnosis of anxiety or active anxiety at some point during pregnancy (would also be 1 if PREGSTART_ANXIETY is 1) (binary variable)	Secondary outcome
PREGANY_PREE	Preeclampsia diagnosed or listed as active problem at any visit while pregnant (binary variable)	Secondary outcome
PNV_COUNT	Number of prenatal appointments attended	Secondary outcome
PNV_TOTSCHED	Number of prenatal appointments scheduled (blank if the same as PNV_COUNT i.e. they didn't cancel any appointments)	Secondary outcome
PREGANY_BEHAVIORALREF	Behavioral health referral at some point during pregnancy (binary variable)	Secondary outcome
PREGANY_SWREF	Social work referral at some point during pregnancy (binary variable)	Secondary outcome
BABY_DISPOSITION	baby's disposition after birth (home health agency, home/self care, children's hospital, cease to breathe, etc)	Exploratory outcome
STILLBORN	whether this baby was stillborn (binary variable)	Exploratory outcome
C_SECTION	Had c-section (binary variable)	Exploratory outcome
BIRTH_WEIGHT	baby's birth weight in grams	Exploratory outcome
NICU_DELIVERYADMISSION	whether the baby was brought to the NICU (binary variable)	Exploratory outcome
ASSUMED_INDUCTION	If a delivery was by c-section prior to 259 days gestation, but there is no documentation of induction then we assume	Exploratory outcome

	it was indicated and this column has a 1 (binary variable). Otherwise, it's 0. Definition came from Hy.	
INDICATED_ONSET	When a delivery form documents that a delivery was induced but not for PROM (binary variable). Definition came from Hy.	Exploratory outcome
CURRENT_PPROM	premature rupture of membranes; diagnosis of O42* during current delivery (binary variable).	Exploratory outcome
VISITNUMBER_F2F	Number of face-to-face visits when pregnant.	Exploratory outcome
PREGANY_PREGINDUCEDHTN_NOPROT	Gestational hypertension without significant proteinuria, could occur during any trimester, childbirth, or puerperium; Diagnosed or listed as active problem at any visit while pregnant. Definition came from EPIC codes	Exploratory outcome
PREGANY_SUPERIMPPREE	Superimposed Preeclampsia diagnosed or listed as active problem at any visit while pregnant (binary variable)	Exploratory outcome
PREGANY_ECLAMPSIA	Eclampsia diagnosed or listed as active problem at any visit while pregnant (binary variable)	Exploratory outcome
PREGANY_UNSPHTN	Unspecified hypertension diagnosed or listed as active problem at any visit while pregnant (binary variable)	Exploratory outcome
PREGANY_ANYHTN	Any hypertension diagnosed or listed as active problem at any visit while pregnant (binary variable)	Exploratory outcome
PREGANY_GDM	Gestational diabetes diagnosed or listed as active problem at any visit while pregnant (binary variable)	Exploratory outcome
CANCELEDVISIT_COUNT	Number of prenatal appointments canceled (blank if 0 appointments canceled)	Exploratory outcome
ANTEPARTUM_EDLD	Number of EDLD visits during pregnancy (EDLD = Emergency Department Labor and Delivery)	Exploratory outcome
ANTEPARTUM_EDTR	Number of ER visits during pregnancy	Exploratory outcome
ANTEPARTUM_ADMISSION	Number of 'IP' or 'OP' hospital visits between pregnancy start date in Epic and delivery	Exploratory outcome
ANTEPARTUM_LOS	Sum of all antepartum admission lengths of stays for each delivery.	Exploratory outcome
POSTPARTUM_EDTR	Number of postpartum visits to ER up to 42 days after pregnancy	Exploratory outcome
POSTPARTUM_ADMISSION	Number of 'IP' or 'OP' hospital visits between delivery date and 42 days postpartum.	Exploratory outcome
POSTPARTUM_LOS	Sum of all postpartum admission between delivery date and 42 days postpartum.	Exploratory outcome
POSTPARTUM_NICU	Provided flags for infant ICU admission within 42 days postpartum.	Exploratory outcome
PP_LOS	postpartum length of stay in hospital in days	Exploratory outcome

Usage metrics

Variable Name	Description
DailyCheckin	Dates of filling out the daily check-in (includes responses to questions on daily mood, number of hours slept, sleep quality, SDOH questions, aspirin adherence, etc)
ArticleReads	Dates of clicking on any article within the app (only after November 2020)
MentalHealthCheckin	Dates of filling out mental health check-in
RelationshipHealthCheckin	Dates of filling out relationship health check-in
SleepHealthCheckin	Dates of filling out sleep health check-in
HelpfulResource	Dates of looking at the helpful resource section (only after November 2020)
HelpfulResourceClick	Dates of clicking on a helpful resource from the helpful resources section (only after November 2020)
OpensApp	Dates of accessing the app at all (best after November 2020, but can also seem many things before November 2020)
Kick Counter	Dates of logging a kick-counting session in Kick Counter section of the app
Contraction Counter	Dates of logging contractions in the Contraction Counter section of the app
Journaling Section (just dates)	Dates of entering a journal into the journaling section of the app
Adding appointment reminders	Dates of adding in an appointment into the Prenatal Visits section of the app

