A Blinded Evaluation of the Effectiveness and Efficacy of the MyHealthyPregnancy Application Statistical Analysis Plan

This study will evaluate the effectiveness and efficacy of the MyHealthyPregnancy App, an app designed to reduce preterm birth risk. This study will use observational cohort data collected at the University of Pittsburgh Medical Center between September of 2019 and February of 2022.

July 18, 2022

[name], [name]

1. Description of the study

MyHealthyPregnancy (MHP) was developed using decision science principles to help prevent preterm birth. An observational cohort trial was conducted at the University of Pittsburgh Medical Center starting in September of 2019 until February 2022. This trial compares the effectiveness of MHP to usual care for pregnant people who delivered at the University of Pittsburgh Medical Center (UPMC). Patients at UPMC were able to download the MHP app after receiving a prescription for the app, as indicated by an EHR variable. Those who were prescribed the app and downloaded it were in the *MHP cohort*. Those who were prescribed the app and did not download it were in the *usual care cohort*. Prescriptions were offered to pregnant people by their care team at an early prenatal visit at UPMC.

EHR data is available for both cohorts of patients. It is the source of all measures, unless otherwise noted.

A linear effects model will be used to evaluate effectiveness by estimating the average treatment effect for the primary endpoint, preventing preterm birth risk.

For each dependent measure, these models will control for primary predictors, as identified in the research literature, that are available in the EHR.

A dose-response model will be used to estimate the effects of continuous measures of non-adherence (as opposed to dichotomous non-adherence, such as not initiating app use). Multiple measures of adherence will be analyzed, including measures of daily use, weekly use, time to initiation, and time from discontinuation to birth.

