1.1.2. Secondary objectives

1. To compare *preterm birth*, defined as delivery before 37 gestational weeks, for the MHP and usual care cohorts. Analyses control for predictors of preterm birth.
2. To compare *depression* rates for the MHP and usual care cohorts, using the clinical diagnosis of depression. Analyses control for predictors of depression.
3. To compare *anxiety* rates across MHP and usual care cohorts, using ICD10 codes. Analyses control for predictors of anxiety.
4. To compare rates of *referrals to behavioral health specialists* for the MHP and usual care cohorts. Analyses control for predictors of behavioral health referrals.
5. To compare rates of *referrals to social workers* for the MHP and usual care cohorts. Analyses control for predictors of social work referrals.
6. To compare rates of *preeclampsia* for the MHP and usual care cohorts. Analyses control for predictors of preeclampsia.
7. To compare *sufficient gestational weight gain*¹ for the MHP and usual care cohorts. Analyses control for predictors of gestational weight gain.
8. To compare the number of *prenatal appointments attended* for the MHP and usual care cohorts. Analyses control for predictors of prenatal appointment attendance.
9. To compare the proportion of *required prenatal appointments attended* in the MHP and usual care cohorts. Analyses control for predictors of prenatal appointment attendance.

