Appendix A contains the full list of each type of measure.

1.2. Study design including blinding

Given the nature of the observational study, patients and providers were not blinded to the treatment condition (MHP, usual care).

The primary statistician will remain blinded to the treatment and usual care cohorts with the exception of using 20% of the unblinded data to evaluate confounders of the outcomes, build a model for propensity score matching, and evaluate confounders of MHP app usage.

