2.3. Treatment Usage

At its current stage of development, the MHP app does not prescribe a set dosage, specifying how often patients should interact with it in order to have desired effects. As such, this study investigates app usage as a mediator of the outcome, rather than comparing users who did and did not meet a predetermined dosage.

We will assess the following aspects of usage: how soon after receiving the prescription participants initiated app use (in days); how soon they discontinued app use prior to delivery (in days since initiation); the percentage of days they used it overall (within the usage period); and the percentage of weeks they used it at least once (within the usage period). See Appendix A for details on these use metrics.

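### Secondary outcomes 4 and 5 count referrals from any point in pregnancy, including those made before the app could act, and the plan lists only proxies to adjust for them

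*SAP*

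**What the plan says.** Appendix A of the SAP defines the two variables as "Behavioral health referral at some point during pregnancy (binary variable" (PREGANY_BEHAVIORALREF) and "Social work referral at some point during pregnancy (binary variable" (PREGANY_SWREF). Section 1.1.2 does not narrow the window; objective 4 compares referral rates "for the MHP and usual care cohorts. Analyses control for predictors of behavioral health referrals", and objective 5 is worded in parallel.

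On exposure, Section 1 states: "Prescriptions were offered to pregnant people by their care team at an early prenatal visit at UPMC". Section 2.3 then measures "how soon after receiving the prescription participants initiated app use (in days", so there is a further interval between prescription and first use.

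Depression and anxiety are also scored over the whole pregnancy, and the depression outcome "would also be 1 if PREGSTART_DEPRESSION is 1". That earlier state has its own baseline covariate, described as "Diagnosed or active depression at first prenatal visit (binary variable", and anxiety has the matching pair. The referral variables have no such counterpart, and no referral date is listed. The sentence just before Section 1.2 says "Appendix A contains the full list of each type of measure".

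Section 3.1.2 names no literature confounder for either referral outcome. Hospital location enters all models (Section 3.1.1). A second model may add baseline covariates that pass a 10% change-in-estimate threshold.

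**The concern.** The outcome window opens when pregnancy begins, but exposure cannot start before the prescription. Any referral made earlier, or at the prescribing visit itself, counts towards the comparison although it precedes any download. Section 3.1.1 limits confounders to baseline variables because the app could not have affected them. The same timing logic should keep events that the app could not have affected out of the outcome.

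Two consequences follow. Download is the woman's own choice, and Section 1.3 concedes that any added encouragement to download is unknown. If need recognised early in care leads both to a referral and to a different chance of downloading, the cohorts differ in early referrals, and that difference appears in the estimated app effect, in either direction. If early referrals are balanced, they add the same events to both cohorts and pull the risk ratio towards 1. Two of the nine tested secondary outcomes are affected; the primary outcome is not.

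**Working it through.** **Inputs from the SAP.** Cohort sizes are 7,147 and 5,197 (Section 1.5, labels blinded). Significance level is 5%, with Bonferroni over nine secondary outcomes (Section 3.1): 0.05/9 = 0.00556, two-sided critical z = 2.773.

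**The plan's own power figure.** It concerns the primary outcome only, but it checks the sample sizes and the sidedness.
- √(1/7147 + 1/5197) = 0.01823
- (1.960 + 0.842) × 0.01823 = 0.0511
- With an SD of 10 days this is 0.51 day, as Section 1.5 states. A one-sided test would give 0.0453, so the plan used a two-sided test.

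**Assumed inputs.** The SAP gives no referral rate, no share of early referrals and no cohort difference in them. Everything below rests on assumed rates and uses unadjusted comparisons.

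**1. Bias, simple form.** Assume no app effect, 15% referred overall, and the whole early difference carried into the outcome.
- SE = √(0.15 × 0.85) × 0.01823 = 0.00651
- 1-point difference: z = 0.01/0.00651 = 1.54; probability of passing 0.05/9 = 1 − Φ(2.773 − 1.54) = 0.11
- 2-point difference: z = 0.02/0.00651 = 3.07; probability = 1 − Φ(2.773 − 3.07) = 0.62

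At 10% overall the SE is 0.00547. The same differences give z = 1.83 (0.17) and z = 3.66 (0.81).

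**2. Bias, allowing for women who would be referred later anyway.** Let b be the early-referral rate and r = 10% the later rate among the rest, equal in both cohorts. The observed rate is b + (1 − b)r. The higher b is placed in the larger cohort.

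| Early rates | Observed rates | Spurious difference | Probability at 0.05 | Probability at 0.05/9 |
|---|---|---|---|---|
| 5% vs 6% | 14.5% vs 15.4% | 0.9 points | 0.28 | 0.08 |
| 5% vs 7% | 14.5% vs 16.3% | 1.8 points | 0.78 | 0.48 |

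For 5% vs 7%: 0.05 + 0.95 × 0.10 = 0.145 and 0.07 + 0.93 × 0.10 = 0.163.

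**3. Dilution.** Assume the app raises later referral from 10% to 12% among women not yet referred (risk ratio 1.20), and early referral is 10% in both cohorts.
- Observed rates: 0.10 + 0.90 × 0.10 = 0.190 and 0.10 + 0.90 × 0.12 = 0.208
- Observed risk ratio: 0.208/0.190 = 1.095, about 1.10
- Power falls from 0.939 to 0.695 at 0.05, and from 0.765 to 0.379 at 0.05/9

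With 5% early referral the observed risk ratio is 0.164/0.145 = 1.13; with 2% it is 0.1376/0.118 = 1.17.

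**The case against.** **The plan does adjust.** This stands in part. Each outcome has an empirical model as well as the literature model, and Sections 1.6 and 3.1.5 add inverse probability weighting and propensity matching. First-visit depression and anxiety, insurance and area deprivation are candidate covariates related to early need. A reader might infer that any difference in intake need passes straight into the reported effect. The documents do not support that, because the proxies may remove some of it. They do not identify who was already referred, so what remains is residual bias.

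**Prescribing cannot separate the cohorts.** This stands. A reader might infer that early need influences who is prescribed the app and so biases the comparison. Both cohorts were prescribed it (Section 1), and being offered a prescription is an inclusion criterion (Section 1.4.1). Only the choice to download can confound.

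**The early window is short and its content unknown.** This stands as a limit on size. Prescription comes early in care, and the SAP neither says how many referrals came before it nor states outright that they are counted. That they are counted is the plain reading of both definitions, and the depression and anxiety outcomes explicitly absorb the first-visit state. Referrals made at the prescribing visit would count however short the window is.

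**A 2-point gap is only one choice.** This also stands: at 1 point the simple calculation does not reach even the uncorrected 5% level (z = 1.54).

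**Conclusion.** The point holds as a flaw in outcome definition. Followed as written, the plan scores referrals that the app cannot have caused, and no listed variable identifies them. The result is residual bias if early referrals differ between women who did and did not download, and dilution if they do not.

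The size cannot be determined from the documents. On the assumed rates, an early-referral gap of 1 to 2 points gives a false positive at 0.05/9 with probability from 0.08 to 0.62 (15% referred overall in the simple form; 5% early in the lower cohort and 10% later in the other). Balanced early referral of 10% cuts a risk ratio of 1.20 to about 1.10. These are unadjusted figures; the planned covariates could reduce the bias by an unknown amount. It would go too far to conclude that the referral comparisons are known to be materially biased, or to predict the direction.

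**What to change.** Have the analyst who holds the cohort labels date each referral in the EHR. In both cohorts, count only referrals dated after the prescription date. If prescription dates are not available for usual care, use the first prenatal visit (PREG_CONTACT_DATE) as the common anchor; this still admits referrals made between that visit and a later prescription. Then choose one of two analyses in advance:

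- restrict both outcomes to women with no earlier referral of that type in this pregnancy; or
- keep all women, count any new later referral, and include a flag for referral on or before the anchor date as a baseline covariate in the outcome models and the propensity score.

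Counting only a first referral after the anchor while keeping women already referred would not work. Those women could never have the outcome, so with 7.5% of them a true 2-point effect in the rest would appear as 2 × (1 − 0.075) = 1.85 points. Keep the whole-pregnancy flags as descriptive variables.

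The cost is one re-extraction, some SAP wording and fewer counted events. It depends on referral dates being available, which the SAP does not confirm; Appendix A lists no referral date, and Section 2.4 mentions data-sharing constraints. If dates cannot be obtained, report the two outcomes as descriptive associations and not as app effects.
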